4 STUDY DESIGN

This is a three-phase study:

1. Cross-sectional, analytical study of the prevalence and patterns of polypharmacy, namely sociodemographic and clinical profiles (age, genre, area of residence and years of study) and about medication (number of drugs and their active component), in older adults attending Primary Care in Portugal.
2. Cross-sectional, triangulation study of older adults' perception of Barriers to and Facilitators of Deprescribing, Willingness to be Deprescribed and Willingness to Self-medicate.
3. Non-pharmacological randomised clinical study of the impact of enablement of older adults in their willingness to be Deprescribed and related Quality of Life.

Phase I: prevalence of polypharmacy in older adults attending primary care in Portugal

Design

Cross-sectional, analytical study.

Setting

Primary Care Centres in Portugal will be randomly selected from the five main-land Portuguese Healthcare Administrative Regions and two Autonomous Regions (Madeira and Azores), in order to obtain a national geographical representative sample.

Sample size

Since the prevalence of polypharmacy in older adults is unknown, we used as base of population all older adults in Portugal. For the study, we used a 95% confidence interval (CI) and a maximum precision error of 5%, so a minimum of 385 patients should be recruited.

Study procedures

This phase of the study starts in November 2017.

General Practitioners (GPs) sampling is made according to existing files of previous projects adherent GPs, in other epidemiological studies. After the selection of GPs, those who accept to participate will recruit their own patients. Assuming that a GP will be able to include at least 6 patients in a 3-week period, a total of 65 GPs will be enrolled in the study: 21 in North of Portugal (31.7%), 16 in Centre of Portugal (24.7%), 18 in Lisbon-Tejo Valley (27.4%), 5 in Alentejo (8.4%), 3 in Algarve (4.3%), 1 in Azores (1.6%) and 1 in Madeira (1.9%) in accordance with the distribution of Portuguese old adult population (≥ 65 years) in Portugal according with Pordata (www.pordata.pt).

Enrolled GPs will be instructed to collect all necessary data about all older adults (≥ 65 years) patients attending a primary care consultation during the period of study: 5 days on 3 consecutive weeks (Monday and Tuesday on week 1; Wednesday and Thursday on week 2; and Friday on week 3).

Data collection

The collection of the data will occur in November 2017.

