GPs will be responsible for collecting all data about patients' sociodemographic characteristics, as well as morbidity and medication, during their consultations.

Data will be electronically stored in a database specifically designed for this study using MS Access 2010. Data will be encrypted and password protected. Information will be treated in strict confidentiality to protect the privacy of patients. The investigators will have no access to the data of the patient, except the one provided by the GP meaning that the only person to know who is being studied is the GP.

Before the collection of data, there will be online reunions with the GPs participating in the study.

Phase II: patients' perception of barriers to and facilitators of deprescribing, willingness to be deprescribed and actual self-medication in adult patients with polypharmacy attending primary care in Portugal

Objectives

To assert reasons and facilitators, willingness to be deprescribed and actual self-medication

Design

Cross-sectional, analytical study.

Setting

It will be the same of the phase I.

Sample size

A minimum of 385 patients will be included in phase II in order to obtain a sample with a 95% CI and a maximum precision error of 5%.

Study procedures

This phase of the study is expected to start in June 2018.

Again, GPs sampling will be made according to existing files and those who accept to participate will recruit their own patients. Patients from phase I can be enrolled in phase II. Assuming that a GP will be able to include at least 6 patients in a 3-week period, a total of 65 GPs has to be enrolled in the study, with the same distribution of the phase I. Enrolled GPs will be instructed to invite all older adult (≥ 65 years) patients attending the primary care consultation to participate in the study during 5 days on 3 consecutive weeks (Monday and Tuesday on week 1; Wednesday and Thursday on week 2; and Friday on week 3). Those willing to participate in the study must give written informed consent and present willingness and ability to comply with the study requirements.

Exclusion criteria will be: Being acutely unwell in the last three weeks, and refuse to participate.

Data collection

The collection of the data will occur in June 2018.

Patient's socio-demographic and clinical characteristics and medication will be registered using the same methodology as described in phase I.

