Perception of medication will be evaluated using Portuguese general BMQ, the willingness to be deprescribed will be assessed with two open-questions (one to assess the facilitators and the other to assess the barriers), and the actual self-medication will be evaluated with an analogic visual scale (0 to 10) about the need to self-medicate and its justification.

For those not knowing how to write or read, someone of their knowledge, will fill in the open questions, with their answers.

In case of less than 5% of answers of the open questions, two patient groups will be invited to make a focus group asserting reasons for accepting deprescribing.

Phase III: impact of enablement of older adults in their willingness to deprescribe and quality of life

Design

Non-pharmacological randomised clinical study, intended to last for six months.

Setting

Primary Care Centres in Portugal will be randomly selected from six Health Centres of Centre of Portugal (Aveiro, Castelo Branco, Coimbra, Guarda, Leiria and Viseu)

Sample size

Will be created two groups with a minimum of 190 patients each (one will be the intervention group and the other the control).

Study procedures

This phase of the study is expected to start in September 2019 and will last for 6 months.

Again, GPs sampling will be made according to existing files and those who accept to participate will recruit their own patients. Patients from previous phases can be enrolled in phase III. Assuming that a GP will be able to include at least 6 patients, a total of 64 GPs has to be enrolled in the study. Enrolled GPs will be instructed to invite all older adult (≥ 65 years) patients attending to the primary care consultation to participate in the study during until obtaining the sample size and being randomized according to the table for study entry. The geographical areas of work, the Districts, will be randomized for entry into exposed and unexposed groups. Those patients willing to participate in the study must give written informed consent and present willingness and ability to comply with the study requirements.

Exclusion criteria: Being acutely unwell in the last three weeks, and refuse to participate.

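### Phases I and II claim a geographically representative national sample from randomly selected centres, but the GPs are volunteers from files of earlier studies, with no stated link to those centres.

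*Protocol*

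**What the plan says.** All of the text is in Protocol section 4.

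- **Phase I, Setting.** "Primary Care Centres in Portugal will be randomly selected from the five main-land Portuguese Healthcare Administrative Regions and two Autonomous Regions". The stated purpose of this draw is that the sample should represent the whole country by area: "in order to obtain a national geographical representative sample".
- **Phase I, Sample size.** "Since the prevalence of polypharmacy in older adults is unknown, we used as base of population all older adults in Portugal". It continues: "we used a 95% confidence interval (CI) and a maximum precision error of 5%, so a minimum of 385 patients should be recruited".
- **Phase I, Study procedures.** GP "sampling is made according to existing files of previous projects adherent GPs, in other epidemiological studies". Of the GPs selected, "those who accept to participate will recruit their own patients". The 65 GPs are allocated to the seven regions by each region's share of the population aged 65 or over. Each GP records every patient of that age who attends on five fixed days spread over three weeks.
- **Phase II.** The Setting is declared the same as in Phase I. The procedures again say "GPs sampling will be made according to existing files and those who accept to participate will recruit their own patients", with the same regional distribution. GPs invite all older attenders, and those who consent are included.

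The Synopsis (section 1.1) calls the first two phases nationwide and gives the prevalence and patterns of polypharmacy as one of their aims.

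**The concern.** The Setting and the Study procedures describe different ways of choosing who contributes data. A random draw of centres gives each centre a known chance of entry and is the usual ground for calling a sample representative. A list of GPs who joined earlier studies, reduced to those who agree again, gives no known chance of entry to GPs in general.

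The protocol does not join the two. It does not say that GPs are sought within the selected centres. It does not say what happens if a selected centre has no GP on the files, or how GPs are picked from the files. Two teams working from this text could run two different surveys.

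What is at stake is the inference from the prevalence estimate in Phase I and from the descriptive results in Phase II. How many drugs a patient takes depends in part on the prescriber. Choosing prescribers by their willingness to do research could therefore affect the quantity being estimated, and enrolling more patients through the same GPs would not remove such an effect.

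**Working it through.** **1. The plan's own sample size.** The inputs from Phase I, Sample size, are 95% confidence and a precision of d = 0.05. No prevalence is stated, so the worst case p = 0.5 is assumed.

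n = z² × p(1 − p) / d² = 1.959964² × 0.25 / 0.0025 = 384.15, rounded up to 385.

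This reproduces the stated figure. The half-width at n = 385 is 1.96 × √(0.25 / 385) = 0.0499, or 4.99 points. The GP count also fits: 385 / 6 = 64.2, rounded up to 65 GPs, and 65 × 6 = 390 patients. The formula assumes a simple random sample from the target population and contains no term for how GPs were selected.

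**2. The regional allocation.** The shares and GP counts are from Phase I, Study procedures.

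| Region | Share (%) | 65 × share | GPs stated |
|---|---|---|---|
| North | 31.7 | 20.605 | 21 |
| Centre | 24.7 | 16.055 | 16 |
| Lisbon-Tejo Valley | 27.4 | 17.810 | 18 |
| Alentejo | 8.4 | 5.460 | 5 |
| Algarve | 4.3 | 2.795 | 3 |
| Azores | 1.6 | 1.040 | 1 |
| Madeira | 1.9 | 1.235 | 1 |
| Total | 100.0 | 65.000 | 65 |

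The allocation is internally consistent, so GP numbers are balanced by region. Two limits remain. Six patients per GP is a minimum and each GP enters all attenders, so the patients' regional shares can drift from the GPs' shares. Azores and Madeira each rest on one GP.

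**3. The two subsections side by side.**

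| Step | Setting | Study procedures |
|---|---|---|
| Unit selected | Primary care centre | GP |
| Source | Seven regions | Files of GPs from earlier studies |
| Mechanism | Random | Not stated, then acceptance by the GP |
| Link to the other step | None stated | None stated |

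**4. What each safeguard covers.** The regional quotas fix how many GPs each region supplies, not which GPs. Recording every attender on fixed days (Phase I) restricts a GP's choice of patients but does not affect which GPs take part. The selection of GPs within a region is covered by neither safeguard, nor by the ±5%.

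**The case against.** The strongest reply is that the protocol claims *geographical* representativeness, and that the proportional quotas deliver it. That stands in part: the quotas are correct and do balance GP numbers by region. But the Setting attributes the property to a random selection of centres, which the procedures do not carry through. The prevalence inference also needs more than the right number of GPs per region.

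A second reply is that these may be two stages, with GPs on file approached inside randomly chosen centres. The text permits that reading but does not state it. Even so, only GPs on the files could enter, and only those who accept would.

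A third reply is that any precision-based sample size covers random error only, and that the protocol never says its ±5% allows for selection. That is correct. A reader might infer that 385 is miscalculated, but it is not.

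A reader might also infer that the national estimate is shown to be biased, or that its interval has some particular lower coverage. The documents do not support this. They give neither the size nor the direction of any difference between these GPs and others, and coverage worked out from an invented bias would look the same for any survey with a ±5-point interval.

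Nor does the point extend to Phase III. Its Setting also pairs randomly selected centres with GPs from existing files, but it claims no national representativeness or prevalence, and GP selection does not in itself affect the between-group comparison.

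**Conclusion.** The point holds as a contradiction with a consequence for inference. The protocol states that randomly selected centres give a geographically representative national sample, then describes recruitment of volunteer GPs from research files with no stated link to those centres. Followed as written, it would attach a nationwide claim to a frame that does not support one. This is more than a missing detail that a statistical analysis plan could supply: such a plan cannot decide which recruitment scheme the protocol prescribes, nor turn volunteers into a probability sample.

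No number can be put on the effect. The 385 is right under simple random sampling at p = 0.5, and its 4.99-point half-width measures random error under that assumption, not distance from the national value. That research-active GPs might differ in prescribing is plausible but is not shown in the document.

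The effect is confined to the descriptive results of Phases I and II. The primary and secondary objectives in section 3 concern enablement, willingness and quality of life, and do not depend on the prevalence estimate. The sponsor should make the change, but it does not threaten the trial's main comparison.

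**What to change.** 1. Reconcile Setting and Study procedures in Phase I, and carry the result into Phase II. If GPs are meant to be sought within selected centres, say so and describe the step.
2. Name the GP file as the sampling frame, and draw GPs from it at random within each region, keeping the present regional counts.
3. Report, by region, how many GPs were approached and how many accepted.
4. Restate the inference in both phases as applying to older attenders of participating GPs from the research file, allocated by region, in place of a randomly selected, nationally representative sample. Describe the ±5% as random error under simple random sampling.

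Weighting the results to the national resident population by age and sex is not a substitute. The Phase I target is people who attend primary care, not all residents, and such weights would not correct for which GPs took part.

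The cost is wording, a random draw from a list that already exists, and a tally of acceptances. The real price is a narrower stated claim. If a phase has already recruited, the draw is no longer available, and the corrected description, the acceptance report (where records allow) and the narrower claim remain.

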1 PROTOCOL SUMMARY

1.1 SYNOPSIS

Title:	Deprescribing: a portrait and out-comes of the reduction of Polypharmacy in Portugal (DePil17-20)
Study Description:	This study protocol comprises three phases. The first two phases will be nationwide and aim to evaluate the prevalence and patterns of polypharmacy and assess the barriers and facilitators of deprescribing perceived by older adults, as well as their willingness to be deprescribed and to self-medicate. The third and last phase will be a non-pharmacological randomised clinical study to measure the impact of enablement of older adults in their willingness to be deprescribed and related quality of life.
Objectives:	Primary Objective: Willingness to be deprescribed after the intervention Secondary Objectives: Quality of life after the intervention
Study Population:	Older adults (≥ 65 years) in Portugal
Description of Study	In the intervention group the investigators will give enablement tools and talks with their General Practitioners about how to issue the problem of polypharmacy.
Intervention:	
Study Duration:	36 months.
Participant Duration:	6 month.

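### Phase II states its self-medication aim both as willingness and as actual behaviour; its one item asks about need, measures neither directly, and is labelled actual self-medication

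*Protocol*

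**What the plan says.** The aim appears in four places in the protocol.

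- Synopsis (1.1), on what the first two phases will assess in older adults: "as well as their willingness to be deprescribed and to self-medicate".
- Section 4, numbered list of phases, second entry: "Willingness to be Deprescribed and Willingness to Self-medicate".
- Section 4, Phase II, Objectives: "To assert reasons and facilitators, willingness to be deprescribed and actual self-medication". The Phase II title uses the same term, actual self-medication.
- Section 4, Phase II, Data collection: "the actual self-medication will be evaluated with an analogic visual scale (0 to 10) about the need to self-medicate and its justification".

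The remaining Phase II data are assigned elsewhere. On the other questionnaire items the protocol says: "Perception of medication will be evaluated using Portuguese general BMQ, the willingness to be deprescribed will be assessed with two open-questions". On the drug record it says: "Patient's socio-demographic and clinical characteristics and medication will be registered using the same methodology as described in phase I". The Phase I entry in the section 4 list describes what is recorded "about medication (number of drugs and their active component", and Phase I makes the GPs responsible for collecting it during consultations.

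**The concern.** Willingness is a disposition, actual self-medication is a behaviour, and need is a judgement about one's own situation. The protocol moves between the three without saying that it regards any two as equivalent, and it attaches the behavioural label to the need rating.

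What is at stake is the meaning of one Phase II result. A mean or distribution on the 0 to 10 scale, written up under the label that the protocol gives it, would be read as a statement of how much older adults in Portuguese primary care self-medicate. The data would show how much they feel they need to. A statistical analysis plan could not repair this later, because it can only analyse what was collected, and the protocol describes no collection of either use or willingness.

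**Working it through.** The point is about what is measured, so no arithmetic applies. The check sets the stated aims beside the data that Phase II will hold.

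**Step 1: what is to be learned**

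| Place | Construct named |
|---|---|
| Synopsis, 1.1 | Willingness to self-medicate |
| Section 4, list of phases | Willingness to self-medicate |
| Section 4, Phase II title | Actual self-medication |
| Section 4, Phase II objectives | Actual self-medication |
| Section 4, Phase II data collection | Labelled actual self-medication; content is need |

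Two places name willingness and two name behaviour. The last takes the behavioural label and describes an item about need.

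**Step 2: what the assigned item can show**

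The protocol describes a 0 to 10 visual analogue rating of need with a reason for it. It gives no recall period, product, frequency or cut-off. Need and the two stated constructs can separate in either direction:

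- A patient may rate need high and take nothing outside the prescribed treatment.
- A patient may take non-prescribed products often and rate need low.
- A patient may be quite willing to self-medicate and at present see no need to.

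The rating therefore does not identify who self-medicates, or who would.

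**Step 3: whether other Phase II data fill the gap**

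| Phase II data | Purpose given | Covers self-medication? |
|---|---|---|
| General BMQ | Perception of medication | Not assigned to it |
| Two open questions | Facilitators of and barriers to deprescribing | Not assigned to it |
| GP drug record, as in Phase I | Number and active component of drugs | Non-prescribed products not mentioned; nothing marks a drug as self-medicated |

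None of the three is assigned to self-medication, and none is described in a way that would yield it.

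**Step 4: reach of the problem**

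Self-medication is absent from the objectives in section 3, the assessments in 7.1, the hypotheses in 8.1 and the Phase III data collection. It is a descriptive element of Phase II only.

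**The case against.** The strongest reply is that the item is more than a score. It also asks for a justification, and patients explaining why they need to self-medicate may say what they take or would take. Felt need may also be a rough proxy for willingness. In addition, the protocol gives only a one-clause summary of the item; the questionnaire wording and anchors are not shown. Finally, the GP record is neither said to include nor said to exclude non-prescribed products.

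Much of this stands, and it limits what can be claimed. A reader might infer that neither aim can be answered at all, or that not one of the 385 patients will supply relevant information. The document does not support that: the justification could reveal use or willingness in some patients, and need could carry some information about willingness. It does not remove the mismatch. As described, the justification explains a felt need and is not a systematic record of use. The protocol does not present need as a proxy for willingness; it calls the item actual self-medication. A drug record that does not flag self-medicated products cannot stand in for the missing measure.

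A reader might also infer that the Phase II sample size is wrong for this aim. The 385 does follow from a single-proportion calculation, taking a proportion of 0.5 as an assumption because the protocol gives none: 1.96² × 0.25 / 0.05² = 384.16, rounded up to 385. A 0 to 10 score is not a proportion. But the protocol sets 385 for Phase II as a whole, does not tie it to self-medication, and nowhere says it will estimate the share of patients who self-medicate. Section 8.3 provides methods for quantitative variables. The sample size gives no ground for criticism on this point.

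**Conclusion.** The point holds in a limited form. Phase II states its self-medication aim in two incompatible ways. The single item assigned to that aim directly measures neither and carries the label of one of them. If the plan is followed, perceived need is reported as behaviour.

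The size is small and has no numerical expression: one descriptive aim in one cross-sectional phase is mislabelled. A reader might infer harm to the trial's main result, since the Phase III information materials are to draw on Phase II knowledge. The protocol does not say that the self-medication item feeds those materials, and self-medication is not a Phase III outcome, so the randomised comparison is unaffected.

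The conclusion rests on two assumptions: that the protocol's summary describes the item fairly, and that no Phase II question on use or willingness exists that the protocol leaves out. A fuller questionnaire containing such a question would reduce the matter to inconsistent wording.

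**What to change.** Choose one construct and use it in the synopsis, the section 4 list of phases, the Phase II title and objectives, and the Phase II data collection text. Then match the item to it in one of three ways:

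- **Actual self-medication:** add a yes/no question on whether the patient took a non-prescribed medicine within a defined recent period.
- **Willingness to self-medicate:** add a question that asks about willingness directly.
- **Perceived need:** keep the present item and restate the aim as perceived need.

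Whichever is chosen, report the 0 to 10 scale and its justification only as perceived need.

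The first two options cost one extra questionnaire item. The third needs no new data and costs a narrower aim. If Phase II data have already been collected with the item as described, only the third remains open.

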Two groups will be created with a minimum of 190 patients each, one of which will be composed from patients from the region of Aveiro, Coimbra and Guarda and the other from patients from the region of Castelo Branco, Leiria and Viseu. In the intervention group we will give enablement tools and talks with their GPs about how to issue the problem of polypharmacy. The information given in this group will result from the knowledge obtained in phase II in the shape of small leaflets and other information materials to be made according to the best practice, to be given and remembered at scheduled times to the intervention group.

Data collection

The collection of the data will occur in the beginning and end of phase II.

Patient's socio-demographic and clinical characteristics and medication will be registered using the same methodology as described in phase I.

Perception of medication will be evaluated using Portuguese general BMQ, the willingness to be deprescribed will be assessed with two open-questions (the same as phase II), and the quality of life we will assessed with EQ-5D.

For those not knowing how to write, someone of their knowledge, will fill in the open questions.

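### The Phase II fallback focus groups ask only why patients would accept deprescribing, so if the barriers question draws few answers nothing is planned to replace it (minor).

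*Protocol*

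**What the plan says.** The two-sided aim appears in several places in the protocol.

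- Section 1.1 (Synopsis): the first two phases are, among other things, to "assess the barriers and facilitators of deprescribing perceived by older adults".
- Section 4, list of phases: Phase II is a "triangulation study of older adults' perception of Barriers to and Facilitators of Deprescribing".
- Section 4, Phase II title: "patients' perception of barriers to and facilitators of deprescribing, willingness to be deprescribed and actual self-medication".
- Section 4, Phase II, Data collection: the instrument is "two open-questions (one to assess the facilitators and the other to assess the barriers".

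Two lines are narrower. The Phase II objectives line reads "To assert reasons and facilitators, willingness to be deprescribed and actual self-medication", without the word barriers. The contingency in Phase II, Data collection, applies when answers to the open questions are below 5%; in that case "two patient groups will be invited to make a focus group asserting reasons for accepting deprescribing".

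Section 4, Phase III, says that the information given to the intervention group "will result from the knowledge obtained in phase II", and that the materials are to follow best practice.

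**The concern.** A fallback should recover what the failed instrument was meant to supply. Here the instrument has two halves and the fallback names a topic for one. A moderator who follows the protocol has an instruction to ask why patients would agree to stop a medicine and none to ask why they would not.

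The missing half matters to this study. The Introduction says that older people may dislike taking many medicines and still be reluctant to stop them, and presents that incongruity as something to be understood. Reluctance is the part that the fallback leaves out. The Phase III intervention is meant to raise willingness, and its content is built from Phase II, so a gap in what is known about barriers would carry into the leaflets.

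**Working it through.** **Coverage of each side.**

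| Source in Phase II | Facilitators | Barriers |
|---|---|---|
| Two open questions | yes | yes |
| Fallback focus groups | yes | not named |
| General BMQ | assigned to perception of medication | assigned to perception of medication |
| Visual scale with justification | assigned to self-medication | assigned to self-medication |

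Only the open questions are assigned to barriers. If the barriers question fails, no other planned source is assigned to take its place.

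**The plan's sample size.** Phase II gives a minimum of 385 patients for a 95% CI and a 5% maximum error. With n = z² p(1 − p) / d², z = 1.96, d = 0.05 and p = 0.5 (the usual worst case, assumed here because the protocol does not state it), n = 384.15, which rounds up to 385. The figure reproduces. It is used below only to turn the 5% into a count.

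**How many barrier answers could be in hand when the fallback starts.** The protocol does not say how the 5% is counted, so each reading is shown.

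1. Per question, with the barriers question below 5%: 0.05 × 385 = 19.25, so at most 19 barrier answers. With the planned 65 GPs × 6 patients = 390, the product is 19.5 and the limit is again 19.
2. Pooled over both questions: 2 × 385 = 770 possible answers and 0.05 × 770 = 38.5, so at most 38 answers in total. Barrier answers number 38 only if every one of them is to the barriers question.
3. Either question below 5%, and only the facilitators question failed: no ceiling on barrier answers, and a focus group on acceptance is a fitting remedy.

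Since 385 is a minimum, the limits in 1 and 2 rise in proportion if more patients are recruited.

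**What those counts can support.** For a coded proportion at p = 0.5 the 95% half-width is 1.96 × √(0.25 / n):

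- n = 19: 1.96 × 0.1147 = 0.225, about 22 points.
- n = 38: 1.96 × 0.0811 = 0.159, about 16 points.

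The planned precision is 5 points. Listing barriers is less demanding than estimating how common they are. If the 19 respondents were a random draw, a barrier held by 10% of patients would appear at least once with probability 1 − 0.9¹⁹ = 0.86, and one held by 20% with probability 1 − 0.8¹⁹ = 0.99. At a response below 5% a random draw is a generous assumption.

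**The case against.** The strongest reply is that the contingency is remote. Patients are recruited by their own GP, give written consent, are taken on as willing and able to comply, and have a helper if they cannot read or write. More than 95% of answers would have to be missing. This stands, and it is the main reason to rate the point as minor. The protocol nevertheless provides for the event, and the provision should fit the aim.

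A reader might infer that the barriers aim would go wholly unanswered. The text does not support that. Nothing says that answers already received are discarded or that the focus groups replace the questions; the word triangulation suggests sources added to one another. Under the third reading above, barrier answers could be plentiful.

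A reader might also infer that the leaflets would rest on facilitators alone. That goes too far as well. They draw on Phase II knowledge as a whole, which includes the BMQ, the justification given with the self-medication scale and any open answers received, and on best practice. None of these is designated a measure of barriers, but together they rule out alone.

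Finally, detailed questions often sit in a topic guide outside the protocol, and participants may raise barriers unprompted. Both are possible. Even so, the topic that the protocol itself sets is one-sided, and a guide written to it would be too.

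**Conclusion.** The point holds in a limited form. If the fallback starts because both questions, or the barriers question, drew few answers, barriers are left with at most 19 written answers out of 385 (counted per question) or at most 38 (pooled) and no planned replacement. The Phase III materials would then be prepared without adequate data on barriers. That is thin evidence, not an absence of evidence.

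The conclusion assumes that the focus groups keep to their stated topic and that about 385 patients are recruited. It does not apply if only the facilitators question fails. The missing word in the Phase II objectives line looks like a slip of language, since the title just above it names barriers; it is an editorial matter and not independent evidence of a design fault.

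Phase III allocation, error rate and power are unaffected. Phase III asks the same two open questions again, but too late to shape the leaflets. This is a minor point.

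**What to change.** 1. In Phase II, Data collection, have both focus groups cover reasons for accepting and reasons for refusing deprescribing.
2. In the same sentence, state whether the 5% trigger applies to each question separately or to both together, and out of what denominator.
3. As an editorial correction, change the Phase II objectives line so that it names barriers and facilitators, as the Phase II title does.

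The cost is three short wording changes and one more topic in a discussion already planned. Sample size and analysis do not change.
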